A sensitivity analysis will be performed excluding any participants recruited in error as per most recent protocol definitions and eligibility criteria.

### **6.3 Missing data**

The amount of missing data is expected to be low (<5%) and a complete case analysis will be conducted.

### **6.4 Additional analyses**

#### *6.4.1. Effect of intervention on cardiorespiratory stability*

A detailed analysis of cardio-respiratory stability will be done for the first 24h of study participation. This will include but is not restricted to a descriptive analysis of: average heart rate; average oxygen saturation; proportion of time spent with abnormal heart rate or oxygen saturation over first day of study participation. Differences between arms will be analysed using Fishers exact tests for categorical variables and two sample *t* test for continuous variables to calculate p values with 95% CI. This may be reported with the primary analysis results or as a secondary analysis.

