#### **3.3 Randomisation and blinding procedures**

##### **3.3.1. Randomisation**

Randomisation will be performed by an independent statistician with computer generated random number tables to give a random allocation of numbers in permuted blocks of varying block sizes. Stratification by admission weight categories will be used with separate random number tables if <1200g or ≥1200g. Allocation concealment will be performed with opaque, sealed envelopes labelled consecutively with the randomisation number (RN00X) and containing a piece of paper stating the randomisation number and the treatment allocation. A research clinician or nurse not connected to the study will prepare the envelopes. The envelopes will be securely kept in a cabinet at the study site office. Following the screening process and collection of baseline data, treatment allocation will take place according to the content of the sealed envelope, in consecutive order of randomisation number. Prior to opening the envelope, the date, time and unique study ID of the baby

Protocol #: 1

---

will be written on the outside of the envelope and the envelope will be stored for later auditing. Subjects who are of twin birth and completed twin admissions will be allocated to the same arm, according to the twin that was declared eligible first. A randomisation log will be kept to ensure that the randomisation procedure is correctly followed.

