## **3.2 Randomisation & allocation**

An independent statistician generated a randomisation sequence using VBA (Visual Basic Application) within an Access database to produce two random number tables with stratification by admission weight categories (<1200g; ≥1200g). Random permuted blocks of varying sizes were used with 1:1 allocation. Allocation concealment was performed with sequentially numbered, opaque, sealed envelopes prepared by an independent researcher and accessible to study team only. Following collection of baseline data, the study nurse opened the next numbered envelope for the correct weight category. The participant identifier, date and time were recorded on the outside of the envelope prior to opening, to identify any subversion of allocation sequence. Twins were allocated to the same arm, according to the first eligible twin's weight.

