**5.6 Adherence to the Standardised Preterm Management Protocol**

Compliance to the standardised preterm/LBW management protocol was monitored daily by the field team and key indicators of standard hospital management were recorded as concomitant medications (E.g. antibiotic therapy, provision of caffeine citrate or aminophylline to prevent apnoea of prematurity). Indicators will be compared between arms from time of study enrolment to discharge or death and will include receipt of key management and investigations. Characteristics will be descriptively summarised with categorical data presented using counts and percentages and continuous data presented using number of patients, mean, median, standard deviation, minimum, maximum and IQR, as appropriate. Data will be presented in the form of a table with arm-specific and total data. Statistical tests comparing concomitant treatments between both arms will be conducted, using Fishers exact tests for categorical variables and two sample *t* test for continuous variables to calculate p values with 95% CIs.

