### **6.5 Harms**

Adverse events and SAEs will be listed and defined with reference to standardised criteria where appropriate. The methods used for data collection and attribution of events will be described.

The number and proportion of participants with an SAE (life-threatening event; risk of disability; re-admission to hospital or prolonged hospital stay >28d) will be presented for both arms. Death will not be included as this is the primary outcome of the trial.

A detailed analysis of blood glucose levels over the first 24h of study participation will be performed as a proxy indicator of disturbance to the IV fluid administration. This will involve number and proportion of participants with hypoglycaemia or hyperglycaemia at defined time points as well as mean glucose level at baseline, 12h and 24h. The significance level will be calculated using chi squared or Fisher's exact tests for categorical variables. Continuous variables will be compared using Student's *t*-test or nonparametric tests, when appropriate. The appropriate effect size will be presented, using risk ratios for binary outcomes and difference between means for continuous data.

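### The between-arm tests for concomitant care, 24-hour heart rate and saturation, and blood glucose ignore same-arm twins and weight-stratified randomisation, so their p-values and confidence intervals are slightly mis-sized, in a direction that depends on the variable

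*SAP*

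**What the plan says.** **Design.** Protocol 3.3.1 says that "completed twin admissions will be allocated to the same arm", and SAP 3.2 confirms it: "Twins were allocated to the same arm". The first eligible twin determines the allocation. Protocol 3.3.1 also says "Stratification by admission weight categories will be used with separate random number tables", and SAP 3.2 describes a sequence built "to produce two random number tables with stratification by admission weight categories", with the cut at 1200g.

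**Tests at issue.** Three sets of between-arm comparisons are specified by named tests:

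- SAP 5.6, concomitant care: "Statistical tests comparing concomitant treatments between both arms will be conducted, using Fishers exact tests for categorical variables" and two-sample t-tests for continuous ones, with p-values and 95% CIs.
- SAP 6.4.1, 24-hour heart rate and saturation: "Differences between arms will be analysed using Fishers exact tests for categorical variables and two sample" t-tests, continuing "test for continuous variables to calculate p values with 95% CI. This may be reported with the primary analysis results" or as a secondary analysis.
- SAP 6.5, blood glucose over the first 24 hours: "The significance level will be calculated using chi squared or" Fisher's exact test for categorical variables, and Student's t or a nonparametric test for continuous ones.

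**Contrast.** SAP 6.2 uses generalised estimating equations (GEE) for binary outcomes, random-effects models for continuous outcomes and a Cox model with frailty for time to death. It also has an analysis adjusted for weight category, gestational age and twin status. No section extends these methods to the three sets above. Protocol 10.3 promises an allowance for clustering in multiple births, but words it for deaths.

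**The concern.** The named tests treat every infant as an independent, simply randomised unit. Two things follow, and they pull in opposite directions.

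- Twins in one arm who resemble each other carry less information than two unrelated infants. The standard error is then too small and the test too liberal.
- Stratified blocks balance weight between arms, but an unadjusted test still counts weight-related variation as noise. The standard error is then too large and the test too conservative for variables linked to weight.

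Heart rate, saturation, glucose and some treatments may plausibly correlate within twin pairs, vary with weight, or both. There is also an internal mismatch. The 24-hour aSCRIP score is built partly from heart rate and saturation (Protocol Appendix III) and is a secondary outcome under SAP 6.2, so it gets a random-effects model. The underlying signals, in the same infants over the same 24 hours, get a two-sample t-test.

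At stake is the reading of borderline results in supportive tables: a false alarm, or a missed imbalance, on co-treatment, saturation or glucose.

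**Working it through.** **Inputs from the documents.** N = 392, 1:1, in permuted blocks of varying size within two weight strata, with twins in one arm (SAP 3.2, 3.3). Threshold p < 0.05 (SAP 4.1), taken as two-sided. The plan states no error rate for these tests. Its one design figure, 392, is reproduced: 48% versus 0.7 × 48% = 33.6%, 80% power, alpha 0.05, with continuity correction, gives 196 per arm. There is no separate allowance for twin clustering.

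**Assumptions (not in the documents).**
- f, the share of infants whose co-twin is also enrolled: 0.1 to 0.4.
- rho, the total within-pair correlation: 0.1 to 0.6.
- R², the share of variance explained by the weight stratum: 0, 5 or 10%.
- 35% of infants below 1200g.
- Both twins in the same stratum; block sizes 2, 4 and 6.

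**Formula.** True variance of the arm difference divided by the variance that the simple test assumes:

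V = (1 − R²) + f × (rho − R²)

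True error rate of a nominal 5% test = 2 × [1 − Φ(1.96 / √V)].

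Worked case: f = 0.3, rho = 0.3, R² = 5% gives V = 0.95 + 0.3 × 0.25 = 1.025 and an error rate of 5.3%.

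**Results for the t-test** (R² = 0 / 5 / 10%). Simulation under no effect: 20,000 replicates, Monte Carlo SE 0.12 to 0.19 percentage points.

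| f, rho | V | Formula, % | Simulated, % |
|---|---|---|---|
| 0.1, 0.1 | 1.010 / 0.955 / 0.900 | 5.1 / 4.5 / 3.9 | 4.9 / 4.6 / 3.9 |
| 0.2, 0.2 | 1.040 / 0.980 / 0.920 | 5.5 / 4.8 / 4.1 | 5.4 / 5.1 / 4.4 |
| 0.3, 0.3 | 1.090 / 1.025 / 0.960 | 6.1 / 5.3 / 4.6 | 5.9 / 5.4 / 4.8 |
| 0.4, 0.6 | 1.240 / 1.170 / 1.100 | 7.8 / 7.0 / 6.2 | 7.8 / 6.9 / 6.3 |

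**Binary variables** (prevalence 10% and 30%, same simulation, R² = 0 / 5 / 10%).

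| f, rho | Chi-squared, % | Fisher, % |
|---|---|---|
| 0.1, 0.1 | 5.1-5.2 / 4.5 / 3.9-4.0 | 4.1-4.4 / 3.5-3.9 / 3.0-3.4 |
| 0.2, 0.2 | 5.4-5.5 / 4.8-5.0 / 4.2-4.4 | 4.5-4.8 / 3.7-4.4 / 3.2-3.9 |
| 0.3, 0.3 | 6.0-6.2 / 5.3-5.5 / 4.5-4.9 | 5.0-5.5 / 4.3-4.8 / 3.7-4.3 |
| 0.4, 0.6 | 7.8-8.0 / 6.8-7.2 / 6.2-6.5 | 6.4-7.1 / 5.8-6.4 / 5.0-5.8 |

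Coverage of an independence-based 95% CI for a risk difference runs from 95.9% (0.1, 0.1, R² = 10%) down to 91.9% (0.4, 0.6, R² = 0).

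**Where the direction turns.** V = 1 when rho = R² × (1 + f) / f. At R² = 5% that is 0.05 × 1.1 / 0.1 = 0.55 for f = 0.1, and 0.30, 0.22 and 0.18 for f = 0.2, 0.3 and 0.4. Above these values the twin effect wins; below them the strata effect wins.

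**Outside the assumed range.** At f = 0.4, rho = 0.8 and R² = 0, V = 1.32 and the error rate is 8.8%.

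**Check of the remedy.** A linear model with the stratum and cluster-robust standard errors by mother gave 4.8-5.3% for continuous and 4.9-5.4% for binary variables in all settings. GEE, the permutation test and the nonparametric option in SAP 6.5 were not simulated.

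**The case against.** The strongest reply is that this hardly matters. In three of the four settings the t-test stays within about one percentage point of 5%. The fourth is not anchored in the documents: each twin must itself meet every criterion (Protocol 4.2), which limits f. The analyses are supportive. SAP 6.4.1 starts from a descriptive analysis under additional analyses, SAP 5.6 summarises descriptively, and SAP 4.1 ties its threshold to the pre-specified outcomes, which do not include these variables. With no multiplicity correction (SAP 4.2), a shift from 5% to between 4% and 6% per test adds little to the false positives expected across many comparisons. Ignoring the strata costs precision but does not create false positives. All of this stands, and it fixes the point as minor. It does not remove it: the sections still promise p-values, and nobody can tell in advance for which variables the two effects cancel.

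Three stronger readings do not hold.

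- A reader might infer that these tests systematically overstate significance. The strata effect can cancel or reverse the twin effect, so no single direction follows.
- A reader might infer from the contrast with SAP 6.2 that the primary and secondary outcomes are free of both problems. The documents do not show that. SAP 6.2 labels the covariate-adjusted analysis primary, then says that the unadjusted result is the primary one, which would leave the weight stratum out there too. It names twins explicitly only for the Cox frailty model.
- Nor do the documents show the opposite, that those outcomes ignore twins. GEE and random-effects models are standard tools for clustering, although SAP 6.2 does not name the cluster for them.

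**Conclusion.** The point holds as a minor one. SAP 5.6, 6.4.1 and 6.5 name tests that use neither the twin allocation nor the weight strata, and nothing elsewhere in the documents corrects this. A nominal 5% t-test has a true error rate of about 4-6% in the low-to-middle settings and up to about 8% in the extreme corner. Chi-squared behaves similarly. Fisher stays at 3.0-5.5% outside that corner and reaches 5.0-7.1% within it. All of these figures rest on the assumed twin share, within-pair correlation and weight association.

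The twin problem is shown only for these three sets of tests. Whether the strata problem also reaches the primary and secondary outcomes depends on how the contradiction in SAP 6.2 is resolved. The SAE counts in SAP 6.5 have no named test, so the point does not touch them. No main conclusion of the trial rests on the affected comparisons.

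**What to change.** In SAP 5.6, 6.4.1 and 6.5, replace the named tests as follows.

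- **Continuous variables:** a linear model with arm and randomisation weight stratum, and cluster-robust standard errors by mother.
- **Binary variables:** GEE or another binary regression with the same terms, clustered by mother.
- **Stratum for twins:** the first eligible twin's, as used at randomisation.
- **Sparse events, or variables needing a nonparametric test:** a permutation test that reassigns arms by mother within stratum.

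Dropping the p-values and reporting these comparisons descriptively would be a simpler alternative.

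**Cost.** SAP wording and minor programming. The regression models are largely those already in SAP 6.2, but the permutation test is an added method. There are enough clusters for robust standard errors: at f = 0.4, 78 pairs + 236 single infants = 314; at f = 0.1, 20 pairs + 352 = 372. SAP 3.5 places the plan's publication before any analyses, so the wording can change then. No trial procedure or sample size changes.

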### **6.5 Harms**

Adverse events and SAEs will be listed and defined with reference to standardised criteria where appropriate. The methods used for data collection and attribution of events will be described.

The number and proportion of participants with an SAE (life-threatening event; risk of disability; re-admission to hospital or prolonged hospital stay >28d) will be presented for both arms. Death will not be included as this is the primary outcome of the trial.

A detailed analysis of blood glucose levels over the first 24h of study participation will be performed as a proxy indicator of disturbance to the IV fluid administration. This will involve number and proportion of participants with hypoglycaemia or hyperglycaemia at defined time points as well as mean glucose level at baseline, 12h and 24h. The significance level will be calculated using chi squared or Fisher's exact tests for categorical variables. Continuous variables will be compared using Student's *t*-test or nonparametric tests, when appropriate. The appropriate effect size will be presented, using risk ratios for binary outcomes and difference between means for continuous data.

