## 1.2 Rationale

Neonatal mortality remains unacceptably high and complications of prematurity are the most common, direct, cause of death in children aged under 5y. Feasible hospital based interventions to reduce mortality in resource limited settings are urgently needed.

The hospital management of preterm/LBW babies is challenging in resource limited settings, for multiple reasons, including: lack of essential newborn care and supportive management; high patient: health care worker ratios and increased risk of hospital acquired infections. Investigation and development of feasible, low cost strategies for the management of these babies within the critical early neonatal period is a global research and public health priority.

Kangaroo mother care is an evidence based and safe intervention currently used for stable newborns <2000g with significant mortality effect. Early, continuous skin-to-skin contact used in unstable newborns has the potential to improve survival through a combination of early and late mechanistic pathways, of which thermal control, cardio-respiratory stability and infection prevention control are the most important.

It is hypothesised that early continuous skin-to-skin contact in mild-moderately unstable neonates will improve survival by:

1. *Early onset, early* impact, stabilisation pathways which improve thermal control, promote cardio-respiratory stabilisation and modulate the natural history of preterm complications.
2. *Early onset, late* impact, pathways include prevention of late-onset infection, promotion of gastro-intestinal stability through improved breast milk feeding and improved recognition of apnoeic events needing resuscitation.

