# **6 STUDY EVALUATIONS**

## **6.1 Clinical evaluations**

### **6.1.1 Evaluations during first 24h of intervention**

All subjects will have continuous cardio-respiratory monitoring with a Nonin 2500A pulse oximeter for minimum 24h after intervention/control procedures begin and continued until the subject is stable (definitions, page 10).

Manual auxiliary temperature will be taken 6hrly for the first 24h. The subjects will be reviewed every 6h for manual recording of the respiratory rate and breathing pattern and reviewed at least once by the study clinician during the initial 24h period. An adapted SCRAP score will be calculated post-hoc to quantify cardio-respiratory stability (Appendix 3). Blood sugar measurements will be measured every 6h, unless  $<2.6$  mmol/l in which case it will be measured 1hrly until 2 or more consecutive readings are in normal range (2.6 – 6.9 mmol/l).

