### **6.1.2 Evaluations from 24h to hospital discharge**

Starting at 48h of study participation, all subjects will be followed up daily until admission to the KMC unit and then weekly on day 7, 14, 21, 28 of life during the KMC unit stay. If a baby requires re-admission to the neonatal unit the reviews will restart every day until KMC unit admission or discharge from the neonatal unit. The following actions will be done using study specific equipment:

- a. Daily review with the following trial assessments documented:
  - Date and time of starting breast milk feeding and date that full breast milk feeding is established
  - Date and time of starting breastfeeding
  - Daily recording of IV fluid volumes, drip rates and medications given
  - Daily measurement of vital signs (heart rate, respiratory rate, oxygen saturation, temperature, blood glucose)
  - Compliance with the standardised management protocol and discussion of any deviations with study site medical team
- Documentation of details about skin-to-skin contact:
  - Date and time of skin-to-skin contact initiation
  - Duration of skin-to-skin contact/day
  - Person providing skin-to-skin contact

Protocol #: 1

- Whether skin-to-skin contact is temporarily discontinued and date/time of this event
- Documentation of patient flow through the ward Identification and documentation of any change in clinical condition warranting temporary cessation of intervention and date/time of temporary cessation
- Identification of any SAE

b. Weighed on day 5, then daily until discharge(to be done at an appropriate time in collaboration with study site staff and clustered with other procedures, E.g. changing of nappies)

c. OFC and length to be measured weekly using study equipment

d. Neonatal skin and rectal swab sample to be taken on days 7 and 28 if still an inpatient or attending outpatient clinic

Study site staff will be responsible for the ongoing medical and nursing management of the neonate according to the standardised management protocol with input from the study team if requested.

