## 8 SAFETY CONSIDERATIONS

### 8.1 Monitoring of study participants

All study participants will undergo continuous cardio-respiratory monitoring for minimum 24h after enrolment and until stability criteria are reached using the Nonin 2500A handheld pulse oximeter, which will measure and record oxygen saturation and heart rate. Alarms will be set to detect bradycardia (heart rate <100 bpm), tachycardia (heart rate >200bpm) and hypoxia (SPO2<88%). If at any stage subjects receiving the intervention have features of severe instability (definitions, page 10) which do not improve with tactile stimulation over 5 minutes, they will be removed from skin-to-skin contact and taken to a radiant warmer for further assessment by the study site health workers.. If the subject responds quickly and vital signs normalise and remain within normal range for 15 minutes, the subject can be returned to skin-to-skin position. If the vital signs do not normalise or the subject requires bag-valve-mask ventilation, the baby will remain on the radiant warmer and receive any appropriate interventions and be temporarily withdrawn from intervention arm (section 11.2). The pulse oximeter will remain attached to the subject until he/she meets criteria for being stable (definitions, page 10) and for 24h after an apnoeic event. If a previously stable baby has a clinical deterioration requiring bag-valve-mask ventilation, or meets criteria for severe instability they will re-commence continuous cardio-respiratory monitoring until 24h after the last episode of bag-valve mask ventilation. If a subject is classed as being severely unstable, a research nurse or study site nurse will contact the research clinician or PI (by telephone if at weekend or night) as soon as possible to inform them of the condition for the participant to be screened for possible infection. The management of the baby will be according to the standardised management protocol, as directed by the study site staff.

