### 8.3 Serious adverse events (SAEs)

The definition of SAE for this study is:

- Death
- Life threatening event
  - Apnoea needing bag-valve-mask ventilation but not resulting in death
  - Severe instability (as per protocol definition)
  - Any other life threatening situation as assessed by clinician
- At risk of permanent / temporary disability
  - Clinically suspected or microbiologically confirmed meningitis
  - Severe jaundice needing phototherapy/exchange transfusion

Protocol #: 1

---

- Suspected Hypoxic Ischaemic Encephalopathy (moderate-severe)
- Acquired hydrocephalus needing diuretics or surgical intervention
- Re-admission to hospital following discharge and within 28d of age
- Prolonged hospitalisation for 28 days or greater

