#### 8.5 Reporting procedures

To monitor for the incidence of adverse events (AE) during the period of hospitalisation, study personnel will review participants daily.

Any adverse events will be recorded in the standardised medical record and eCRF, including any treatments used by study site staff. Study site staff will be responsible for treating any AE with input from the research clinician and PI, as requested. The research clinician will review all AE and classify serious adverse events according to the protocol. All SAE will be reviewed by the PI or delegate within 24h of notification.

The PI or delegate will send an initial notification to the local safety monitor (LSM), sponsor and Clinical Trials Support Office at MRCG within 24h of first being aware. The initial detailed SAE report will be sent to LSM, sponsor and CTSO within 2 working days if the baby dies, or within 5 working days if the baby does not die. The DSMB will receive a 2 monthly summary safety report of all SAE's, as per DSMB charter. Any SAE thought to be related to the intervention will be reported to the ethics committees within 7 days if it results in death or 14 days if non-fatal. All SAE's resulting in death but not related to

Protocol #: 1

the intervention will be submitted to ethics committees as a monthly summary. All other (non-fatal) SAE's will be reported as an annual safety report to ethics committees and the sponsor.

Reporting procedures will be outlined in an Adverse Event SSP. All SAE reports or other safety reports will be kept as essential documents in the Trial Master File.

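### Severe instability and bag-valve-mask apnoea are watched for less closely once a baby is stable, yet SAP 6.5 tabulates SAEs by arm with no common monitoring window

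*SAP*

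**What the plan says.** **The harms table.** SAP 6.5 will show, by arm, "The number and proportion of participants with an SAE (life-threatening event; risk of disability" followed by re-admission and prolonged stay. On fatal events it says: "Death will not be included as this is the primary outcome of the trial". It gives no observation window, person-time denominator or split by monitoring status. Re-admission and stays beyond 28 days are counted, so the table must reach past the first day.

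**The events.** Protocol 8.3 names two specific life-threatening SAEs. One is severe instability as defined in the protocol; the other is "Apnoea needing bag-valve-mask ventilation but not resulting in death".

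**The surveillance.** Protocol 6.1.1 schedules oximetry for "minimum 24h after intervention/control procedures begin and continued until the subject is stable". Protocol 8.1 has the same rule: "The pulse oximeter will remain attached to the subject until he/she meets criteria for being stable" (and for 24h after an apnoeic event). From 48h, under Protocol 6.1.2, "all subjects will be followed up daily until admission to the KMC unit and then weekly on day 7, 14, 21, 28 of life". SAP 3.6 gives the same daily-then-weekly schedule. Protocol 8.5, on adverse events during hospitalisation, says instead that "study personnel will review participants daily".

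**The hypothesis.** Protocol 1.2 and SAP 2.2 expect the intervention to promote cardio-respiratory stabilisation. Protocol 1.2 also lists "improved recognition of apnoeic events needing resuscitation" among its expected effects.

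**The concern.** How long a baby stays under alarmed monitoring, and when review drops from daily to weekly, depends on becoming stable. That happens after randomisation and is something the intervention is meant to change. Using the same stopping rule in both arms does not give equal surveillance if one arm meets the rule earlier.

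The trial is unblinded and safety is its third objective, so readers will look at the SAE table. If one arm shows fewer participants with severe instability or bag-valve-mask apnoea, the table as planned cannot separate fewer events from fewer events noticed.

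**Working it through.** **Step 1. Surveillance by period, from the documents.**

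| Period | Oximetry | Study review |
|---|---|---|
| First 24h after procedures start | Continuous in both arms (Protocol 6.1.1, 8.1) | Every 6h (6.1.1) |
| After 24h, not yet stable | Continuous (6.1.1, 8.1) | Daily from 48h (6.1.2) |
| Stable, neonatal unit | Off | Daily (6.1.2) |
| KMC unit | Off | Weekly under 6.1.2 and SAP 3.6; daily under 8.5 |

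Only the first row has a length fixed by design. Oximetry restarts after bag-valve-mask ventilation or severe instability (8.1), which helps to catch later events. SAP 6.5 counts participants with an SAE, so the first event matters most.

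**Step 2. Which components depend on the monitor.** The alarm limits in Protocol 8.1 (SpO2 below 88%, heart rate below 100 or above 200) are also elements of the severe-instability definition. Protocol 14.3.1 gives timely detection as a purpose of the oximeters. Meningitis, jaundice, re-admission and prolonged stay do not depend on them.

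**Step 3. Size from lost detection.** The documents give no SAE rate, time to stability or detection rate, so there is no figure of the plan to reproduce here and the inputs are assumptions. Let true risk be equal in both arms and detection on oximetry complete. Let *s* be the detection probability off oximetry, and f the share of first events that occur off oximetry (fE in the arm stabilising earlier, fL in the other).

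Apparent risk ratio = [1 − fE(1 − s)] / [1 − fL(1 − s)]

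| fE vs fL | s = 0.5 | s = 0.75 | s = 0.9 | s = 1 |
|---|---|---|---|---|
| 40% vs 20% | 0.80/0.90 = 0.89 | 0.90/0.95 = 0.95 | 0.96/0.98 = 0.98 | 1.00 |
| 60% vs 30% | 0.70/0.85 = 0.82 | 0.85/0.925 = 0.92 | 0.94/0.97 = 0.97 | 1.00 |

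**Step 4. Reversal if caregivers notice more.** Suppose the intervention arm is the earlier one (40% vs 20%), and skin-to-skin contact raises its off-monitor detection to 0.9 against 0.5 in control. The ratio is (1 − 0.4 × 0.1)/(1 − 0.2 × 0.5) = 0.96/0.90 = 1.07.

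**Step 5. Time in which to record a non-fatal SAE.** Planned 28-day mortality is 48% in control (SAP 3.3) and 48% × 0.7 = 33.6% with the intervention. In the feasibility study 10 of 14 deaths fell in the first week (Protocol 1.1). Assume those deaths are spread evenly over days 0–7 and the rest over days 7–28.

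- Mean day of death: (10/14) × 3.5 + (4/14) × 17.5 = 7.5
- Control: 0.52 × 28 + 0.48 × 7.5 = 18.2 days alive
- Intervention: 0.664 × 28 + 0.336 × 7.5 = 21.1 days alive
- Ratio: 21.11/18.16 = 1.16

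Because death is left out of the table, the arm with better survival has about 16% more time in which to record an SAE. This is time alive, not time in hospital.

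**The case against.** The strongest reply is that little is missed. Monitoring ends only when a baby holds SpO2 of at least 88% in room air. After that, severe instability requires SpO2 below 88% in oxygen with another sign, or CPAP, and the apnoea SAE requires bag-valve-mask ventilation. Each of these involves a staff action that would normally be recorded. Staff are also asked to report apnoea and any new oxygen or CPAP need (Protocol 6.1.3, Figure 3). This stands as a limit on size and makes high values of *s* plausible. It does not make *s* equal to 1, because staff must first notice the episode, and the alarm that would prompt them is off.

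Secondly, Protocol 2.1 ties the safety objective to cardio-respiratory stability at 24h. The aSCRIP in Appendix III scores need for bag-valve-mask ventilation and low saturation, and SAP 6.4.1 analyses heart rate and saturation over the first 24h. A reader might infer that the SAE table is the main safety result; the documents do not say so. Neither of those 24h analyses counts participants with these SAEs, however, so the gap in SAP 6.5 remains.

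Thirdly, SAP 6.5 only presents the SAE proportions; the tests it names belong to the glucose analysis. That is correct, but figures set out by arm will be compared.

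Finally, an arm that stabilises sooner may truly have fewer such events. That also stands, and the planned table could not tell this from under-detection.

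**Conclusion.** The point holds as a limit on interpretation. Ascertainment of two SAE components depends partly on a post-randomisation state, and SAP 6.5 sets no window in which surveillance is scheduled alike.

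A reader might go further and infer that the arm stabilising sooner will look safer. The documents do not support that. Lost detection lowers that arm's count (ratio 0.82 to 0.98 for off-monitor detection of 0.5 to 0.9, and no effect at 1). Better recognition by caregivers and longer survival can each raise the intervention arm's count. Nor do the documents make oximetry the main detector of these events, or say that the table covers exactly the hospital stay.

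The ratios rest on assumed shares and detection probabilities, and the survival figure on planning mortality and an assumed spread of deaths. Net direction and size cannot be determined. If clinical staff pick up nearly all events off the monitor, the detection bias is close to zero. The change is worth making because it is cheap.

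**What to change.** In SAP 6.5:

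1. Keep the full-period SAE proportions by arm and state the period they cover.
2. Alongside them, add a by-arm comparison of severe instability and bag-valve-mask apnoea in the first 24h after procedures start, when both arms are scheduled for continuous oximetry. Use the generalised estimating equations already planned for binary outcomes, and show deaths in that window by arm.
3. Report hours on continuous oximetry by arm, and label the full-period figures for these two components as subject to unequal monitoring.
4. Do not compare arms on events per monitored hour. After 24h that denominator is largely time spent not yet stable, so the comparison would condition on post-randomisation instability.

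Protocol 6.1.2 and 8.5 must be reconciled on whether review on the KMC unit is weekly or daily, and the report should state what was done.

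The cost is SAP wording and one extra table. Oximeter recordings are already stored (Protocol 11.1.3); the table also assumes that SAE records carry event times, which the documents do not state. The 24h window will hold fewer events and says nothing about late ones, which is why the full-period row stays.
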